## PROTOCOL SYNOPSIS

Protocol Number	ACP-103-055	
EudraCT Number	2018-003252-20	
Protocol Title	A 52-Week Open-Label Extension Study of Pimavanserin in Subjects With Major Depressive Disorder and Inadequate Response to Antidepressant Treatment	
Name of Investigational Product	Pimavanserin tablets	
Indication	Adjunctive treatment of major depressive disorder	
Phase of Development	3	
Sponsor	ACADIA Pharmaceuticals Inc. 	
Primary Objective	To assess the safety and tolerability of long-term pimavanserin treatment in subjects with major depressive disorder and inadequate response to antidepressant treatment	Primary Endpoint Treatment-emergent adverse events (TEAEs)
Exploratory Objectives	
 
• To explore the safety and tolerability of long-term pimavanserin treatment in subjects with major depressive disorder and inadequate response to antidepressant treatment on the following:                             
 
○ suicidality
 
○ extrapyramidal symptoms
 
○ general health assessments
 
 
 
• To explore the benefits of long-term pimavanserin treatment in subjects with major depressive disorder and inadequate response to antidepressant treatment on the following:                             
 
○ improvement of depression symptoms
 
○ clinical global impression of severity of depressive symptoms
 
 
 
	Exploratory Endpoints Safety and tolerability endpoints: 
 
• Columbia–Suicide Severity Rating Scale (C-SSRS)
 
• Extrapyramidal Symptom Rating Scale–Abbreviated (ESRS-A) score
 
• Sexual dysfunction defined as a CSFQ-14 total score of <math>\leq 47</math> for men and <math>\leq 41</math> for women
 
• Vital signs
 
• Body weight
 
• Potentially clinically important laboratory values
 


 
○ functional impairment
 
○ sexual functioning
 
	
Efficacy endpoints:
 
 
• Change from Baseline in Hamilton Depression Scale (17 items) (HAMD-17) total score
 
• Treatment responder rates. Treatment response is defined as a reduction from Baseline in HAMD-17 total score of 50% or more.
 
• Treatment remission rates. Treatment remission is defined as a HAMD-17 total score <math>\leq 7</math>.
 
• Change from Baseline in Clinical Global Impression–Severity (CGI-S) score for depressive symptoms
 
• Change from Baseline in Sheehan Disability Scale (SDS) score
 
• Change from Baseline in the Changes in Sexual Functioning Questionnaire Short Form (CSFQ-14) score
 
• Change from Baseline in Karolinska Sleepiness Scale (KSS) score
 

Number of Study Sites	Up to approximately 80 sites will participate in this study.
Number of Subjects Planned	Up to approximately 420 male and female subjects from the antecedent studies, Study ACP-103-054 and Study ACP-103-059
Test Product, Dose, and Administration	Pimavanserin 34 mg is provided as 2×17 mg tablets. It is recommended that the subject should take the study drug at approximately the same time each day. Tablets will be administered orally as a single dose once daily.
Study Design	
This study will be a 52-week open-label extension study to evaluate the long-term safety and tolerability of pimavanserin in subjects with major depressive disorder and inadequate response to antidepressant treatment.
 
The study will have two periods (Figure S-1):
 
 
• Open-label treatment period (52 weeks)
 

	
 
• Safety follow-up period (at least 30 days)
 
 
The end of treatment (EOT) visit for the antecedent study, Study ACP-103-054 or Study ACP-103-059, is the Baseline visit for the present study.
 
Open-label Treatment Period (Baseline through Week 52)
 
Eligible subjects will begin pimavanserin once-daily dosing at 34 mg.
 
During the treatment period, clinic visits will be conducted at Baseline and Weeks 2, 4, 8, 12, 16, 28, 40, and 52 (EOT), or upon early termination (ET) from the study.
 
Study drug will be dispensed to the subject to take home at the Baseline visit. The subject will be instructed to take the first dose of study drug on the day after the Baseline visit.
 
All concomitant permitted medications should remain stable during the study, including the background antidepressant.
 
Safety Follow-up Period (30 Days)
 
A safety follow-up telephone call to the subject will be conducted at least 30 days after the last dose of study drug.
 
The schedule of assessments is provided in Table S-1.

Study Duration
	
The duration of participation for individual study subjects will be up to approximately 56 weeks.
 
Each subject will participate in a 52-week treatment period followed by a safety follow-up period of at least 30 days (Figure S-1). The study completion date is defined as the date the final subject, across all sites, completes their final protocol-defined assessment, which includes the safety follow-up visit/contact.
 
The total duration of exposure to pimavanserin may be greater than 52 weeks (e.g., up to 58 weeks) as subjects may have been treated with pimavanserin in a previous study.

Main Criteria for Inclusion and Exclusion
	
To be eligible for this study subjects must meet all of the inclusion and none of the exclusion criteria.
 
Inclusion Criteria:
 
 
1. Completed the antecedent study, Study ACP-103-054 or Study ACP-103-059
 

[figure not shown]
	

2. May benefit from longer term therapy with open-label pimavanserin treatment in the judgment of the Investigator

3. Is willing and able to provide informed consent. Consent for the present study must be obtained prior to the procedures being performed at the Week 6/EOT visit of Study ACP-103-054 or Study ACP-103-059

4. Is capable of communicating with the site personnel, able to complete subject-reported outcome measures and can be reliably rated on assessment scales (in the opinion of the Investigator)

5. If the subject is female, she must not be pregnant or breastfeeding. She must also be of non-childbearing potential (defined as either surgically sterilized or at least 1 year postmenopausal) OR must agree to use TWO clinically acceptable methods of contraception during the study and 1 month following completion of the study. Acceptable methods of contraception include the following:

a. A barrier method (condom, diaphragm, or cervical cap) with spermicide

b. Hormonal contraception, including oral, injectable, transdermal, or implantable methods

c. Intrauterine device (IUD)

Only one of the two clinically acceptable methods can be a hormonal method.

 
Exclusion Criteria:
 

1. Is judged by the Investigator or the Medical Monitor to be inappropriate for the study, due to adverse events, medical condition, or noncompliance with investigational product or study procedures in Study ACP-103-054 or Study ACP-103-059, or is judged to be a danger to self or others

2. Has any of the following electrocardiogram (ECG) results at Baseline (i.e., Week 6/EOT visit of Study ACP-103-054 or Study ACP-103-059):

a. If the subject is not on citalopram, escitalopram, or venlafaxine (immediate or extended release):

--	--

	

i. QTcF >450 ms, if QRS duration <120 ms

ii. QTcF >470 ms, if QRS duration <math>\geq</math>120 ms

b. If the subject is on citalopram, escitalopram, or venlafaxine (immediate or extended release):

i. QTcF >425 ms, if QRS duration <120 ms

ii. QTcF >450 ms, if QRS duration <math>\geq</math>120 ms

3. Has a heart rate (as measured by peripheral pulse rate) <50 beats per minute at Baseline (i.e., the Week 6/EOT visit of Study ACP-103-054 or Study ACP-103-059) not explained by regular exercise or medication, in discussion with the Medical Monitor

4. Has a body mass index (BMI) <18.5 kg/m^2 or known unintentional clinically significant weight change (i.e., +/- <math>\geq</math>7% of body weight) in Study ACP-103-054 or Study ACP-103-059 as assessed by the Investigator

5. Has clinically significant laboratory abnormalities that, in the judgment of the Investigator or Medical Monitor, would either:

a. jeopardize the safe participation of the subject in the study; OR

b. would interfere with the conduct or interpretation of safety or efficacy evaluations in the study

6. Is suicidal as defined below at Visit 1 (Baseline) of the present study:

a. An answer of “yes” to C-SSRS questions 4 or 5 (current or over the last 6 months); OR

b. Has attempted suicide within 1 year prior to Visit 1 (Baseline); OR

c. Is actively suicidal in the Investigator’s judgment

7. Has developed delirium or a neurologic, cardiovascular, respiratory, gastrointestinal, renal, hepatic, hematologic, or other medical or mental disorder, including cancer or malignancies that, in the judgment of the Investigator or the Medical Monitor, would increase the risk associated with

--	---

	
taking study medication or significantly interfere with the conduct or interpretation of the study
 
8. Requires treatment with a medication or other substance that is prohibited by the protocol
 
9. Has a significant sensitivity or allergic reaction to pimavanserin or its excipients
 
10. Is an employee or is a family member of an employee of ACADIA Pharmaceuticals Inc.


Sample Size Calculations
	
It is estimated that approximately 420 subjects from Studies ACP-103-054 and ACP-103-059 will be eligible to enter this study. The sample size for this study is not based on statistical power, but will depend on the number of subjects who transition into this open-label extension study from the antecedent studies, Study ACP-103-054 and Study ACP-103-059.

Statistical Methods
	
The purpose of this study is to collect safety data from subjects exposed to pimavanserin for up to 52 weeks in this study. Exploratory objectives include assessment of efficacy outcome measures over time. No statistical testing is planned.
 
All endpoints will be summarized for the Safety Analysis Set. Additional summaries by prior treatment may be included.
 
Data from the EOT visit procedures of Study ACP-103-054 and Study ACP-103-059 will be carried over as baseline information in the present study, as applicable.
 
Descriptive Statistics
 
Continuous measurement results will be reported using the number of subjects with data values, mean, standard error of the mean, median, standard deviation, minimum, and maximum. For each categorical outcome, the frequency and percentage of subjects in each category will be reported.
 
Primary Analyses
 
All adverse events (AEs) will be classified into standard terminology using the Medical Dictionary for Regulatory Activities (MedDRA). All AEs will be listed and TEAEs will be summarized by system organ class and preferred term. A TEAE is defined as an AE that started after the first administration of study drug and no later than the last administration of study drug plus 30 days. Summaries by

	
maximum severity and by relationship to study drug will also be provided. Serious TEAEs, fatal AEs, and TEAEs leading to discontinuation will also be summarized.
 
Exploratory Analyses
 
For the C-SSRS, the number and percentage of subjects with suicidal ideation or suicidal behavior during this study will be tabulated.
 
Descriptive summary statistics for ESRS-A observed values and change from Baseline will be provided by timepoint.
 
Number and percentage of subjects with sexual dysfunction (a total score of <math>\leq 47</math> for men and <math>\leq 41</math> for women) will be summarized and shift tables will be presented.
 
Descriptive summary statistics for vital signs and body weight, and potentially clinically important laboratory values, including observed values and changes from Baseline will be tabulated by timepoint.
 
Descriptive summary statistics for HAMD-17, CGI-S, SDS, CSFQ-14, and KSS observed values, and change from Baseline will also be provided by timepoint.
 
Treatment responder rate and treatment remission rate will be summarized by timepoint.
 
Other Safety Analyses
 
Descriptive summary statistics for ECG observed values and changes from Baseline will be tabulated by timepoint. Additionally, categorical analyses will be conducted on the incidence of subjects with prolonged QTc intervals and changes in QTc intervals in accordance with International Council for Harmonisation (ICH) guidelines and Food and Drug Administration (FDA) E14 guidance document.

Date	11 August 2020

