## 2.2 Exploratory Objectives

The exploratory objectives of this study are:

- To explore the safety and tolerability of long-term pimavanserin treatment in subjects with major depressive disorder and inadequate response to antidepressant treatment on the following:
  - suicidality
  - extrapyramidal symptoms
  - general health assessments
- To explore the benefits of long-term pimavanserin treatment in subjects with major depressive disorder and inadequate response to antidepressant treatment on the following:
  - improvement of depression symptoms
  - clinical global impression of severity of depressive symptoms
  - functional impairment
  - sexual functioning

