## **9.5.2 Exploratory Analyses**

For the C-SSRS, the number and percentage of subjects with suicidal ideation or suicidal behavior during this study will be tabulated.

Descriptive summary statistics for ESRS-A observed values and change from Baseline will be provided by timepoint.

Number and percentage of subjects with sexual dysfunction (a total score of  $\leq 47$  for men and  $\leq 41$  for women) will be summarized and shift tables will be presented.

Vital sign measurements and body weight, including changes from Baseline, will be summarized by timepoint using descriptive statistics. The number and percentage of subjects with changes from Baseline (increases and decreases separately) in body weight of  $\geq 7\%$  will also be provided by timepoint.

Clinical laboratory parameters, including changes from Baseline, will be summarized by timepoint using descriptive statistics. For selected parameters, the number and percentage of subjects with potentially clinically important post-baseline laboratory values will be summarized by timepoint as well as across all post-baseline timepoints. The criteria for potentially important values will be specified in the SAP.

Descriptive summary statistics for HAMD-17, CGI-S, SDS, CSFQ-14, and KSS observed values, and change from Baseline will be provided by timepoint.

Treatment responder rate and treatment remission rate will be summarized by timepoint.

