5.1 General Data Reporting Conventions

For continuous variables, the following summary statistics will be provided: number of subjects, mean, standard error of the mean (SE), standard deviation (SD), minimum, maximum, and median. Unless specified otherwise, means, and medians will be presented to one more decimal place than the raw data, and the SDs and SEs will be presented to 2 more decimal places than the raw data.

For categorical variables, summaries will include the number and percentage of subjects in each category, using the number of subjects with non-missing values as the denominator for the percentages (unless otherwise specified). Categories with zero counts will not have zero percentages displayed. Percentages will be presented to 1 decimal place.

When converting number of days to months, it will be calculated as the number of days divided by 365.25 and then multiplied by 12. When converting number of days to years, it will be calculated as the number of days divided by 365.25.

No hypothesis testing is planned. Descriptive summaries of all safety and efficacy endpoints will be provided.

All safety and efficacy endpoints will be summarized for the Safety Analysis Set. In addition, summaries by treatment group according to the original double-blinded treatment actually received in the antecedent study (placebo or pimavanserin) will also be provided.

For each continuous measure in safety and efficacy analyses, change from Baseline results will be presented in two ways:

1. Main analysis: using the Baseline from Study ACP-103-055 and reporting the changes across Study ACP-103-055 timepoints
2. Exploratory analysis: using the Baseline from the antecedent study (ACP-103-054 or ACP-103-059), and reporting the changes across Study ACP-103-055 timepoints

For the treatment responder rate, the summary will also be presented in two ways:

1. Main analysis: using the Baseline from Study ACP-103-055 and reporting the rate across Study ACP-103-055 timepoints
2. Exploratory analysis: using the Baseline from the antecedent study (ACP-103-054 or ACP-103-059), and reporting the rate across Study ACP-103-055 timepoints

The treatment remission rate and the percentage of subjects with sexual dysfunction will also be summarized across Study ACP-103-055 timepoints using the Baseline from Study ACP-103-055 and the Baseline from the antecedent double-blind studies as reference points.

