13 METHODS OF EFFICACY ANALYSES

Descriptive statistics for all efficacy endpoints listed in [Section 12.1](#) including treatment responder and remission rates will be tabulated by the double-blind treatment group in the antecedent studies at scheduled timepoints. The summaries of the change from Baseline results will be presented in two ways (main analysis and exploratory analysis) as specified in [Section 5.1](#).

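### The by-visit remission rate mixes remission already present at open-label entry with remission gained later, and no analysis described in the SAP separates new, maintained and lost remission

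*Protocol*

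**What the plan says.** - **Definition.** Protocol Synopsis, Efficacy endpoints: "Treatment remission is defined as a HAMD-17 total score" of 7 or less. Protocol 2.2.1 and SAP 12.1 say the same. Response, listed beside it, is a 50% reduction from Baseline; remission has no Baseline term.
- **Analysis in the protocol.** Section 9.5.2: "Treatment responder rate and treatment remission rate will be summarized by timepoint".
- **Analysis in the SAP.** Section 5.1: "The treatment remission rate and the percentage of subjects with sexual dysfunction will also be summarized across Study ACP-103-055 timepoints", with the open-label Baseline and "the Baseline from the antecedent double-blind studies as reference points". Section 13 adds that efficacy endpoints "including treatment responder and remission rates will be tabulated by the double-blind treatment group in the antecedent studies at scheduled timepoints".
- **Denominator.** The general rule in SAP 5.1 is "using the number of subjects with non-missing values as the denominator for the percentages". Nothing in SAP 12 or 13 overrides it for remission, and SAP 12.3 does not impute missing total scores.
- **Who is counted.** SAP 4 uses the Safety Analysis Set throughout. Protocol 4.1 and 4.2 set no HAMD-17 threshold for entry.
- **Timing of Baseline.** The open-label Baseline is the antecedent study's end-of-treatment visit, and the first open-label dose is taken the next day (Protocol 3.1 and 5.1.3).
- **Purpose.** Protocol 2.2: "To explore the benefits of long-term pimavanserin treatment in subjects with major depressive disorder".

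**The concern.** A subject who finishes the antecedent study at a HAMD-17 total of 7 or less and then does not change is counted as in remission at every open-label visit. For a prior-placebo subject, that remission came before any open-label pimavanserin. The visit rate is therefore a point prevalence made up of two groups: subjects who arrived in remission and kept it, and subjects who reached it during the extension.

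For an objective about the benefit of long-term treatment, these groups answer different questions. One is how many entry non-remitters later remit. The other is how many entry remitters later exceed 7. A single by-visit percentage answers neither, and quoting a Baseline percentage next to it does not fully answer them either. No tests are planned, so the descriptive tables are the evidence, and a reader may take a Week 28 or Week 52 rate as remission gained on open-label drug.

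**Working it through.** The documents give no remission rate at any visit, so there is no figure of the plan's own to reproduce. Every rate below is an assumption.

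**1. Does the choice of Baseline change a visit rate?** The numerator is the number of subjects with a visit total of 7 or less. The denominator is the number with a non-missing total at that visit. Neither uses a Baseline value, so the post-Baseline rate is the same under both. A simulation with invented scores (420 subjects, 30% missing at Week 52) shows this:

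| | Open-label Baseline | Antecedent Baseline |
|---|---|---|
| Remission at that Baseline | 25.3% | 0% |
| Week 52 remission | 123/288 = 42.7% | 123/288 = 42.7% |
| Week 52 response | 30.6% | 59.0% |

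The response rate moves with the Baseline and the Week 52 remission rate does not. The remission rates at the two Baselines do differ, so displaying them adds information.

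**2. What does the visit rate contain?** In the same simulation the 123 remitters were 67 already in remission at open-label Baseline and 56 new ones (67 + 56 = 123). Of 73 entry remitters with Week 52 data, 6 had lost remission (67 + 6 = 73). The by-visit rate shows none of this split.

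For a rough size, take 15% to 35% in remission at entry, 80% of them still in remission at a visit, and the same subjects at both times. The pre-existing part is then 0.15 × 0.80 = 0.12 to 0.35 × 0.80 = 0.28, or 12 to 28 percentage points of that visit's rate.

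**3. Can the two rates recover the movement?** Let p0 be the entry rate, p1 the visit rate and j the proportion in remission at both, in the same subjects. Then max(0, p0 + p1 − 1) ≤ j ≤ min(p0, p1).

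- Loss among entry remitters = 1 − j/p0.
- New remission among entry non-remitters = (p1 − j)/(1 − p0).

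With p0 = 0.30 and p1 = 0.45, j lies between 0 and 0.30. Loss then runs from 1 − 0.30/0.30 = 0% to 1 − 0/0.30 = 100%. New remission runs from 0.15/0.70 = 21.4% to 0.45/0.70 = 64.3%.

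The range is not always this wide. With p0 = 0.40 and p1 = 0.20, j is at most 0.20, so loss is at least 1 − 0.20/0.40 = 50%. A large net fall does reveal loss.

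**4. Dropout.** Take 100 subjects, 30 in remission at entry. Thirty non-remitters leave and nobody else changes. The rate goes from 30/100 = 30% to 30/70 = 42.9% with no new remission. Protocol 4.4 lists lack of efficacy among the reasons for discontinuation, and SAP 3.5 and 3.6 record that the study was stopped early.

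**5. Do other described analyses fill the gap?**

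- SAP 8 cuts Baseline HAMD-17 at 24, not at 7.
- SAP 12.5 subgroups are age, sex and antidepressant type, for change scores only.
- Response from open-label Baseline classes a stable remitter as a non-responder: a subject entering at 6 must fall to 3.
- Protocol 9.5.2 plans shift tables for sexual dysfunction, the other fixed-cutoff endpoint, but none for remission.

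**The case against.** The strongest reply is that an absolute cutoff by visit is a legitimate prevalence summary, that it attributes nothing to the drug in an uncontrolled study, and that the plan gives more context than a quick reading suggests. Four stronger criticisms that a reader might infer are not supported.

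- **That the SAP promises two remission presentations with identical figures.** SAP 5.1 presents change scores and the responder rate in two ways, but uses the Baselines for remission only as reference points. SAP 14.6.3 tabulates sexual dysfunction at the antecedent Baseline visit alongside the open-label timepoints. The natural reading for remission is one set of visit rates with Baseline rates beside it. Only the post-Baseline rates must coincide, and that is not itself an error.
- **That remission on placebo is hidden by pooling.** Remission is tabulated by antecedent treatment. If Baseline rates are shown, the prior-placebo column carries its own.
- **That worsening cannot be seen.** It can appear in a net fall in the rate, in HAMD-17 and CGI-S change from open-label Baseline, in discontinuation reasons and in the listings of all data.
- **That no such table exists anywhere.** SAP 1 places table specifications in a separate document, so the point is limited to what the SAP describes.

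It is also fair that the 0% to 100% range is a mathematical extreme for one chosen pair of rates, and that early stopping will thin any shift table at late visits.

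What remains is that Baseline rates beside visit rates still do not separate new, maintained and lost remission, and that observed-case rates can drift through dropout.

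**Conclusion.** The point holds as a cheap improvement to an exploratory, descriptive endpoint. By-visit remission includes remission already present at open-label Baseline, some of it reached on placebo. The reference Baselines cannot alter any post-Baseline rate, and no analysis described in the SAP separates subjects by entry status.

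The size is unknown because the documents give no entry remission rate. The 12 to 28 points rest on assumed entry rates of 15% to 35% and assumed 80% persistence, and are illustrative only. The bounds in step 3 are exact for the rates assumed there and require the same subjects at both times; dropout and early stopping weaken that condition.

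No primary result, test or decision rule is affected. It would be wrong to conclude that the remission definition is invalid or that worsening on treatment would go unnoticed.

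**What to change.** In SAP 5.1 and 13:

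1. Keep the by-visit remission rate, and state that the reference points mean the remission rate at each Baseline is displayed beside it.
2. Add a shift table of remission status at open-label Baseline (7 or less, above 7) by status at each visit, overall and by antecedent treatment. Report (i) the percentage in remission among subjects above 7 at open-label Baseline and (ii) the percentage above 7 among subjects at 7 or less at open-label Baseline. Limit denominators to subjects with data at both timepoints and print them.

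This adds to the Baseline reference rates and does not replace them. In the dropout example it would show 0 of 40 remaining non-remitters newly in remission and 0 of 30 remitters lost, in place of an apparent rise from 30% to 42.9%. It does not remove selection through dropout, but it stops that selection from looking like new remission.

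The cost is some SAP wording and one extra table from data already collected. The downside is small denominators, particularly by arm at late visits, because the study stopped early.
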